4.3. Justification for Dose

The dose levels planned for this study were selected based on the totality of PK, safety, and efficacy data from the Study 18001. See Section 2.2 for efficacy results and Sections 2.2 and 2.3 for safety results.

Three dose levels were selected to compare the currently approved 200-mg dose to 2 lower dose levels. Based on the available data, the proposed doses for this study are 200 mg, CCI CCI

The chosen dose levels are anticipated to provide an exposure range that is pharmacologically active and provide an opportunity to observe any meaningful differences in efficacy or safety.

An assessment of the exposure (PK)-response relationships for safety and efficacy indicated a wide therapeutic window of concentrations for pirtobrutinib supporting the proposed dose levels of 200 mg, CCI

Safety results showed a safe and tolerable profile across all doses tested, with no dose-limiting toxicities, and no maximum tolerated dose was identified.

Data supporting 200 mg QD dose

The 200-mg dose is approved for use by the FDA for patients with CLL/SLL, who have received at least 2 prior lines of therapy, including a BTK inhibitor and a BCL2 inhibitor. This dose level was based on a well-tolerated safety profile, PK analyses consistent with a compelling level of target engagement as predicted by nonclinical models, and promising and durable antitumor activity.

At the 200-mg dose, CCI of participants are predicted to exceed 90% inhibition of BTK at steady state based on population PK simulation.

For the CLL/SLL populations previously treated with BTK inhibitors, the overall response rate to a starting dose of 200 mg QD is CCI based on IRC assessments.

Data supporting CCI QD doses

CLL/SLL populations previously treated with BTK inhibitors achieved a response rate of CCI based on IRC assessments in participants with a starting dose of 25 mg QD to 100 mg QD CCI CCI

Approximately CCI of participants at the CCI dose and approximately CCI of participants at the CCI are predicted to exceed 90% inhibition of BTK at steady state based on population PK simulation.

Dose proportionality

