6.6.1. Guidelines for Adjusting or Withholding or Discontinuing Study Intervention to Manage AEs

The investigator may adjust the participant’s dose or temporarily or permanently discontinue the participant from study intervention if the participant experiences a clinically significant AE as assessed by NCI CTCAE v5.0.

These principles guide investigators on when to adjust the 200-mg or CCI, or withhold, or discontinue the study intervention due to AEs.

Pirtobrutinib exhibits linear PK. The current guidance to manage AEs is to reduce the pirtobrutinib exposure level.

For participants receiving 200 mg QD, the reduction to 100 mg QD is equivalent to a 50% exposure reduction from the starting dose. A further reduction to 50 mg QD is equivalent to a 50% exposure reduction from 100 mg QD.

For participants receiving CCI QD, the reduction to CCI QD is equivalent to a CCI exposure reduction from the starting dose of CCI QD.

This table provides guidance to manage AEs.

Adverse Events	Occurrences Requiring Dose Modification	Pirtobrutinib Dose Modification Instructions		
		200 mg	CCI	

 Grade 3 or greater non-hematologic toxicity^a Absolute neutrophil count <1 to $0.5 \times 10^9/L$ with fever and/or infection Absolute neutrophil count $<0.5 \times 10^9/L$ lasting 7 or more days Platelet count <50 to $25 \times 10^9/L$ with bleeding Platelet count $<25 \times 10^9/L$ 	First occurrence	Hold pirtobrutinib until recovery to Grade 1 or baseline. May restart at original dose level. ^b		
	Second occurrence	Hold pirtobrutinib until recovery to Grade 1 or baseline. May restart at 100 mg ^c	Hold pirtobrutinib until recovery to Grade 1 or baseline. May restart at CCI ^c	Discontinue
	Third occurrence	Hold pirtobrutinib until recovery to Grade 1 or baseline. May restart at 50 mg ^c	Discontinue	
	Fourth occurrence	Discontinue		

Dose modification is not recommended for asymptomatic lymphocytosis. Asymptomatic lipase increase may not necessarily warrant dose modification.

^a Evaluate the benefit-risk before resuming treatment at the same dose for a Grade 4 non-hematological toxicity.

^b If a Grade 3 or Grade 4 treatment-related AE takes longer than 21 days to recover to Grade 1 or baseline, reduce the dose after the first occurrence.

^c If the dose was reduced previously for the same event, continue to the next lower dose level or discontinue.

The investigator should also refer to the IB for the current safety information.

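### Footnote b of the dose-modification table calls for a dose reduction after a slow-recovering first toxicity, but one arm has no lower level and the footnote gives no alternative

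*Supplement*

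**What the plan says.** The trial has three arms (protocol Section 4.3): "Three dose levels were selected to compare the currently approved 200-mg dose to 2 lower dose levels". The two lower doses are redacted.

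Section 6.6.1 sets out the handling of adverse events in a table with three dose columns and a row for each occurrence.

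- **First occurrence.** A single instruction appears: hold until recovery, then "May restart at original dose level". It carries footnote b, under which, if a Grade 3 or 4 treatment-related event "takes longer than 21 days to recover to Grade 1 or baseline, reduce the dose after the first occurrence". The footnote names no arm.
- **Second occurrence.** The 200 mg column restarts at 100 mg, the next column restarts at a redacted level, and the third column reads *Discontinue*. The two restart cells carry footnote c: "If the dose was reduced previously for the same event, continue to the next lower dose level or discontinue".
- **Text above the table.** Reductions are described for the 200 mg arm, "For participants receiving 200 mg QD, the reduction to 100 mg QD is equivalent to a 50% exposure reduction from the starting dose" and "A further reduction to 50 mg QD is equivalent to a 50% exposure reduction from 100 mg QD", and for one other arm, "For participants receiving CCI QD, the reduction to CCI QD is equivalent to a CCI exposure reduction from the starting dose of CCI QD". No such sentence exists for a third arm.

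The end of Section 6.6.1 limits a hold for treatment-related toxicity to 28 days from the last dose, with a longer delay possible in exceptional circumstances if the sponsor agrees. Section 6.6 describes the recommendations as a guide that leaves investigator judgment in place.

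**The concern.** Footnote b assumes that every arm it covers has a level to step down to. One arm appears to have none. A site there, with a participant whose first related Grade 3 event recovers on day 24, reads a footnote asking for a reduction and a column that offers no reduced dose. The site must then decide for itself whether to resume at the same dose or to stop.

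That choice determines what is recorded. Sections 3 and 9.3.4 list discontinuations, interruptions and reductions due to an adverse event among the secondary safety measures, summarized by dose level. Section 2.1 gives the purpose of the trial as finding out whether a lower dose improves safety without loss of efficacy. If identical events in one lower-dose arm become an interruption at one site and a discontinuation at another, part of the tolerability contrast reflects how sites read a footnote rather than the dose. The study is open-label, so sites also know which arm they are dealing with.

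**Working it through.** The plan gives no figure to reproduce. The check is a cell-by-cell reading of Section 6.6.1, followed by one line of arithmetic on scale.

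**Step 1. Count the reduced levels in each arm.**

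| Arm (table column) | Reduced levels given | Second occurrence | Can footnote b be followed? |
|---|---|---|---|
| 200 mg | 2 (100 mg, then 50 mg) | restart at 100 mg | yes |
| second column (redacted) | 1 (redacted) | restart at a redacted level | yes |
| third column (redacted heading) | 0 | *Discontinue* | no |

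Footnote b needs at least one reduced level. Two of the three arms have one.

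**Step 2. Is this an effect of the redaction?** The two deciding elements, the wording of footnote b and the third column's *Discontinue*, are both legible. Two inferences remain.

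- The third column is taken to be the lowest dose because the reduced levels fall 2, 1, 0 across the columns and both other doses are below 200 mg.
- The first-occurrence instruction is taken to span all columns because no other first-occurrence text exists. This rests on the table layout as extracted.

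If the label were wrong, one arm would still lack a reduced level.

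**Step 3. Does another footnote fill the gap?** Footnote c pairs the next lower level with discontinuation as an alternative. Footnote b has only the reduction.

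**Step 4. Can the situation arise?** Footnote b starts after 21 days, and the ordinary hold limit is 28 days. If both clocks start at about the same time (an assumption, since one counts time to recovery and the other counts from the last dose), the window runs from day 22 to day 28. Longer holds need sponsor agreement, and Section 7.1 lists a delay beyond 28 days for hematologic toxicity as a reason to stop. The gap therefore matters mainly within that window.

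**Step 5. Scale.** Inputs: 249 participants (Section 9.5) and equal allocation (assumed, since the ratio is redacted).

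- Participants per arm: 249 / 3 = 83.
- Effect of one participant recorded as a discontinuation rather than an interruption only: 1 / 83 = 0.012, about 1.2 percentage points of that arm's rate.
- For k such participants: k / 83. The documents give no usable value of k, because the Study 18001 adverse event counts are redacted and no recovery times are shown.

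**The case against.** The strongest reply is that the table can be read sensibly as it stands. Footnote b brings forward the step normally taken at the second occurrence, and in the third column that step is *Discontinue*. The introduction to the table may point the same way: "These principles guide investigators on when to adjust the 200-mg or CCI, or withhold, or discontinue the study intervention due to AEs". If the hidden text names a single dose, adjustment may be meant for two arms only. This reading is plausible, but it is not written down. The introduction cannot settle it while the dose is redacted, and footnote b itself does not restrict the arms. A site could equally conclude that the footnote does not apply to its participant and resume at the original dose.

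A second reply is that these are guidelines. That stands in part. A reader might infer that footnote b is a binding order and that every course open to the site breaches the protocol. The documents do not support that. Section 6.6 keeps investigator judgment, Section 7.1 allows discontinuation for safety reasons, and a permission to restart is not breached by stopping. But that latitude is also why two sites can reasonably record the same event differently, so it does not close the gap.

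A third reply is that dose changes and their reasons are recorded in the CRF. This helps in interpreting the counts afterwards. It does not make the sites' actions uniform.

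**Conclusion.** The inconsistency is real and narrow. In the arm without a reduced level, footnote b cannot be followed as written, mainly when a first related Grade 3 or 4 event recovers between about day 22 and day 28. Discontinuations and interruptions due to adverse events in that arm may then depend partly on site interpretation. The conclusion rests on the extracted table layout and on the inference that the third column is the lowest dose.

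The number of participants affected cannot be estimated from the documents. With equal allocation assumed, each one is worth about 1.2 percentage points of that arm's discontinuation rate. A reader might infer a shift of 10 to 20 points by assuming that 10 to 20% of the arm meets the trigger. No rate in the documents supports that assumption, it overlooks the 28-day limit, and it requires every case to be resolved in the same direction.

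A reader might also infer a loss of responses in that arm. That is not supported either. The estimand in Section 3 handles treatment discontinuation by treatment policy, and Section 1.3 continues disease assessments after discontinuation until progression or alternative cancer therapy. The point rests on the inconsistency and on the safety endpoints alone.

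**What to change.** The sponsor should reconcile footnote b with the third column of the Section 6.6.1 table, so that every arm has one stated action when recovery of a first event exceeds 21 days. This could be done by wording footnote b for each column, or by limiting it to the columns that have a reduced level and giving the remaining column its own note. What that action should be is a clinical decision for the sponsor, and none is proposed here. The CRF dose-action instruction should then be aligned with the revised text so that the same event is coded the same way at every site.

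The cost is one footnote in a protocol amendment and a matching CRF instruction, with no added procedures or participants.

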6.6.1.1. Guidelines for Resuming a Treatment Cycle after Management of AE Toxicity

In the event of dosing interruptions due to toxicity, and subsequent restarting of pirtobrutinib, the cycle schedule and radiologic imaging schedule will not change.

Before resuming the next treatment cycle, AE toxicity must resolve to Grade ≤ 1 or baseline.

Exceptions include AEs with no immediate medical consequence that can be controlled with adequate treatment. Examples of such AEs include pain, alopecia, neuropathy, fatigue, nausea, vomiting, diarrhea, Grade 2 hypothyroidism, or Grade 2 hypertension.

6.6.2. Guidelines for Re-escalating Study Intervention

For participants who have undergone a dose reduction of pirtobrutinib, investigators may

- re-escalate their dose once the participant tolerates a reduced dose of pirtobrutinib for ≥ 2 weeks without toxicity, or
- maintain that dose, even if there is minimal or no toxicity with the reduced dose.

A re-escalation should not exceed the original starting dose.

If the AE that led to the dose reduction was not related to study intervention, the investigator may consider repeat re-escalations, not to exceed the starting dose, if tolerated.

6.7. Continued Access to Study Intervention after the End of the Study

Once criteria are met for the end of study, participants may have the opportunity to continue receiving pirtobrutinib in an open-label extension study or if pirtobrutinib is commercially available.

6.8. Treatment of Overdose

In the event of an overdose, the investigator or treating physician should

- contact the medical monitor immediately
- evaluate the participant to determine, in consultation with the medical monitor, whether study intervention should be interrupted or whether the dose should be reduced
- closely monitor the participant for any AE/SAE and laboratory abnormalities as medically appropriate until, for example, if a participant experiences an SAE because of a drug overdose the SAE should be reported immediately or within 24 hours from the knowledge of the event

- in the event that the overdose is associated with an SAE, the 2 events should be linked and the SAE reported as detailed in Section 10.3.5, and
- document the quantity of the excess dose and the duration of the overdose in the CRF.

For this study, an overdose is defined as any dosage that exceeds the maximum dosage in the protocol. There is no known antidote for overdose of pirtobrutinib. In the case of suspected overdose, monitor hematology, chemistry, and vital signs and provide supportive care as necessary and notify the sponsor.

6.9. Prior and Concomitant Therapy

Concomitant therapy data collection

For therapy that the participant is receiving at the time of enrollment or receives during the study, whether prescription or over-the-counter, authorized study personnel should collect

- the name of medication, vaccine, or therapy
- the reason for use
- route of administration, and
- dates of administration, including start and end dates.

Contact the medical monitor if there are any questions regarding concomitant or prior therapy.

6.9.1. Allowed Concomitant Therapy

Anticancer medications

Continuation of certain anticancer medications, such as hormonal therapy for participants with prior prostate cancer or breast cancer, is allowed. Examples of these anticancer medications include

- Gonadotropin-Releasing Hormone or Luteinizing Hormone-Releasing Hormone agonists
- aromatase inhibitors, or
- selective estrogen receptor modulators or degraders.

Steroids

Steroid use is allowed only in these conditions unless approved by the sponsor

- brief, limited use of systemic corticosteroids (≤ 7 days), where such use is considered standard of care, such as premedication for contrast allergy, short courses to treat asthma, and for chronic obstructive pulmonary disease
- chronic use of steroids (> 7 days) to treat symptoms from an immune-related AE
- systemic glucocorticoid use
 - to treat symptoms of an immune-related AE
 - for prevention of emesis
 - to premedicate for IV contrast allergies or reactions
 - as short-term oral or IV use in doses > 10 mg/day prednisone equivalent to treat asthma or COPD exacerbations, and

- as chronic systemic replacement doses, not to exceed 10 mg/day prednisone equivalent
- other glucocorticoid use
 - topical or ocular
 - intraarticular, and
 - inhalation for the management of asthma or COPD, and
- local steroid injections.

Vaccines

Killed vaccines are allowed.

Any licensed COVID-19 vaccine, including for Emergency Use, in a particular country is allowed if they are mRNA vaccines, adenoviral vaccines, or inactivated vaccines.

6.9.2. Prohibited Concomitant Therapy

Pirtobrutinib is a substrate of CYP3A. Concomitant medications that are strong inhibitors and strong or moderate inducers of CYP3A should be avoided as these agents may alter the exposure of pirtobrutinib. Pirtobrutinib is also a P-gp inhibitor, a moderate CYP2C8 and BCRP inhibitor, and a weak CYP2C19 and CYP3A inhibitor. Concomitant use of pirtobrutinib with sensitive P-gp, CYP2C8, BCRP, CYP2C19, or CYP3A substrates may increase their plasma concentrations, which may increase risk of AEs related to these substrates for drugs that are sensitive to minimal concentration changes.

Section 10.8 includes a table that summarizes potential drug-drug interaction risks and examples of commonly used oral medications in that drug class that should not be coadministered with pirtobrutinib during the study.

The following additional medications and vaccinations are prohibited during the study:

- any investigational product not specified in this protocol
- systemic anticancer agents not specified in this protocol
- herbal drugs known to have antitumor activity. Herbal agents are considered to have anticancer activity if they are included in local treatment guidelines or have randomized clinical data demonstrating benefit
- glucocorticoids except for use as noted in Section 6.9.1
- medications or vaccinations specifically prohibited in the exclusion criteria (Section 5.2)
- live or live attenuated vaccines within 30 days before the first dose of study intervention and 90 days after the last dose of study intervention, and
- investigational vaccines, that is, those not licensed or approved for Emergency Use, with the exception of COVID vaccines.

Medications or vaccinations specifically prohibited in the exclusion criteria (Section 5.2) are not allowed during the ongoing trial. If there is a clinical need for the participant to have any prohibited medication or vaccine, the investigator must consult with the sponsor's medical monitor.

Upon the observation of AEs following coadministration of pirtobrutinib with other medications, consult the product labels of pirtobrutinib and the concomitant drug(s) and consider adjusting dose or discontinuing the coadministered drug(s), as appropriate.

The final decision on any supportive therapy or vaccination rests with the investigator and/or the participant's treating physician.

6.9.3. Concomitant Therapy for Infections or Bleeding

See Section 8.2.7 for more information on monitoring for infections and bleeding.

Infections

The use of prophylactic antimicrobial therapy should be considered in all study participants when clinically appropriate. Local practices or guidelines regarding infection prophylaxis should be followed.

Prophylactic antibiotic or IV immunoglobulin therapy for management of participants at risk of infections may be considered. Initiation of prophylactic antibiotics against pneumocystis infection before study intervention administration may be warranted.

Examples of antimicrobial therapy include

- trimethoprim-sulfamethoxazole
- dapsone
- aerosolized pentamidine, and
- atovaquone.

Bleeding

The benefit versus risk of concurrent treatment with anticoagulation and antiplatelet therapy should be carefully considered for participants who require this therapy.

If a participant needs surgery, the benefit versus risk of withholding anticoagulation or antiplatelet therapy for at least 3 to days before and after surgery should be considered depending upon the type of surgery and the risk of bleeding.

The sponsor recommends withholding pirtobrutinib for at least 3 days before and after surgery where bleeding risk cannot be excluded.

6.9.4. Radiation Therapy

Local treatment while receiving study intervention, for example, palliative radiation therapy for symptomatic nodal disease, is permitted if the participant is not considered to be clinically or radiologically progressing. If the lesion that is to be treated is a target lesion, the lesion will be censored at the time of treatment. However, the participant may remain on study provided there is other evidence of disease that can be followed for determination of progression.

7. Discontinuation of Study Intervention and Participant Discontinuation/Withdrawal

Discontinuation of specific sites or of the study as a whole are handled as part of Section [10.1](#).

7.1. Discontinuation of Study Intervention

When necessary, a participant may be permanently discontinued from study intervention. If so, the participant will discontinue the study intervention (treatment) and will remain in the study to complete procedures for all remaining study visits, as shown in the SoA.

A participant should be permanently discontinued from study intervention if

- the participant or the participant's designee requests to discontinue study intervention
- the participant is noncompliant with study procedures or treatment
- there is disease progression determined by the investigator per iwCLL 2018 criteria. Sponsor verification of progressive disease may be requested
- the participant requires alternative treatment, unless the treatment is temporary, such as local radiation or surgery to relieve symptoms of the disease that does not otherwise meet the definition of disease progression
- there is a dose delay of more than 28 days for hematologic toxicity. In exceptional circumstances, a longer delay is permitted upon agreement between the investigator and the sponsor. See Section [10.7](#)
- the participant becomes pregnant during the study, or
- in the opinion of the investigator, the participant should permanently discontinue the study intervention for safety reasons.

If the participant, for any reason, requires treatment from another therapeutic agent that is effective for the study indication, discontinuation from study intervention will occur prior to introduction of the new agent. If medically appropriate, complete the short-term follow-up procedures before introduction of the new agent; see Section [1.3](#).

If a participant has confirmed disease progression recorded and has discontinued study intervention, the participant will be followed up for survival status until death, withdrawal of consent for survival status, or the end of the study.

See Section [6.6](#) for additional guidelines for discontinuing study intervention.

